2.2. Background on Bladder Cancer and Rationale for the Study

The purpose of this study is to characterize the safety and mechanisms of action of CPX-POM in patients with newly diagnosed or recurrent, untreated or intravesical treatment completed >6 months before the current diagnosis, resectable bladder tumors.

Bladder cancer is the sixth most common solid tumor in the United States with an estimated 80,479 new cases and 17,670 deaths in 2019 ([American Cancer Society, 2019](#)). In 2016, there were an estimated 699,450 people living with this disease in the United States ([Siegel et al, 2019](#)). The disease has a high risk of recurrence as well as progression, thus requiring

life-long surveillance, making bladder cancer one of the most expensive cancers to treat on a per-patient-lifetime-basis (Botteman et al, 2003; Yeung et al, 2014). While the overall 5-year survival rate for bladder cancer is 77%, in those with advanced disease, this rate can be as low as 4% (NCI SEER Cancer Stat Facts, 2019).

Bladder cancer is defined as two diseases, each with different treatment approaches as well as outcomes. Seventy percent or more of newly diagnosed patients have non-muscle invasive bladder cancer (NMIBC) which is generally considered less life-threatening than muscle invasive bladder cancer (MIBC) (Heneý, 1992). However, in spite of endoscopic resection followed by intravesical immunotherapy (Bacillus Calmette-Guérin [BCG]) or chemotherapy (e.g., mitomycin C, gemcitabine), 60 to 70% of those with NMIBC will recur and 20 to 30% will progress to MIBC (Aldoursari and Kassouf, 2010), where the gold standard treatment is radical cystectomy (RC) coupled with cisplatin-based chemotherapy in either neoadjuvant or adjuvant settings (Milan-Rodriguez et al, 2000). It is estimated, however, that as many as 40 to 50% of MIBC patients are ineligible for cisplatin chemotherapy due to impaired renal function (Dash et al, 2006). Patients with impaired performance status (Eastern Cooperative Oncology Group [ECOG] >1), heart failure (New York Heart Association [NYHA] class \geq III), grade \geq 2 hearing loss, and/or grade \geq 2 neuropathy are also ineligible for cisplatin-based chemotherapy. Given the poor complete response rate associated with neoadjuvant carboplatin and gemcitabine (Peyton et al, 2018), cisplatin-ineligible MIBC patients go straight to RC or enroll in clinical trials.

CPX, the active metabolite of CPX-POM, has been shown to be active against both MIBC and NMIBC in vitro. In vivo, CPX-POM treatment of mice with established bladder tumors induced by N-butyl-N-(4-hydroxybutyl)-nitrosamine (BBN) resulted in robust antitumor activity. More importantly, CPX has been shown to have inhibitory activity against the Notch signaling pathway. Notch overexpression is associated with bladder cancer cell growth and survival. Inhibition of Notch may be an important target for the control of bladder cancers. Finally, currently available agents are administered topically by intravesical administration. Approximately 50% of NMIBC cases will recur within 12 months and 25% will progress to MIBC. CPX-POM affords an opportunity to develop a targeted, systemically administered therapy for NMIBC patients who are at risk of progressing to MIBC as well as a neoadjuvant treatment for MIBC in cisplatin-ineligible patients.

CPX-POM potentially has several major advantages over CPX and CPX-O in the context of treatment for bladder cancer: 1) CPX-POM represents a composition of matter patentable invention; 2) CPX-POM possesses much improved physical and chemical properties that enable injectable formulation development; 3) by developing an injectable formulation of CPX-POM, CicloMed hopes to avoid the dose-limiting gastrointestinal toxicities and poor oral bioavailability observed following oral CPX-O administration; 4) CPX-POM is rapidly metabolized to CPX, which is eliminated in the urine as a glucuronide conjugate; 5) elevated beta-glucuronidase activity in the urine of bladder cancer patients has the potential to

hydrolyze the conjugate back to CPX and thereby affords the potential to target CPX to the bladder epithelium; and 6) CPX-POM administered systemically has the potential to deliver drug to the entire urinary tract (i.e., to treat upper urinary tract disease), as opposed to agents delivered by bladder instillation.

The Investigator's Brochure provides further details of the nonclinical studies and published clinical evaluations of CPX-POM ([CPX-POM Investigator's Brochure, 2019](#)).

3. OBJECTIVES

The primary objective is:

- To characterize the safety and dose tolerance of CPX-POM administered as 900 mg/m² IV by 20-minute IV infusion once daily for 5 days to patients with newly diagnosed or recurrent bladder tumors who will be scheduled to undergo transurethral resection of a bladder tumor (TURBT)

The secondary objectives are:

- To determine the number of patients with treatment-related AEs
- To elucidate mechanisms of CPX-POM action on bladder tumor tissues employing an unbiased approach, using ribonucleic acid sequencing (whole transcriptome shotgun sequencing, RNA-seq) and chromatin immunoprecipitation-DNA sequencing (ChIP-seq)
- To determine the change in bladder tumor tissue cell proliferation, Notch and Wnt cell signaling pathways, as well as bladder tumor tissue CD8⁺ tumor-infiltrating lymphocytes (TIL) via immunohistochemistry
- To determine bladder tumor tissue-to-plasma and tissue-to-urine CPX concentration ratios

The exploratory objective is:

- To determine urine β -glucuronidase activity

4. STUDY DESIGN

4.1. Overall Design

This will be an open-label study to determine the safety, dose tolerance, PK, and PD of CPX-POM in patients with newly diagnosed or recurrent, untreated or intravesical treatment completed >6 months before the current diagnosis, resectable tumors. Approximately 12 patients will be enrolled and treated with 900 mg/m² CPX-POM administered IV over 20 minutes once per day for 5 days followed by TURBT on Day 5 after the fifth dose. TURBT will be performed 2 to 6 hours following drug administration on Day 5.

Pretreatment bladder tumor tissues will be obtained at the time of in-office cystoscopy by cold cup biopsy within 4 weeks of TURBT. Posttreatment bladder tumor tissues will be obtained at TURBT. Bladder tumor tissues will undergo pathological evaluation at each site.

Prior to administration of the first CPX-POM dose on Day 1, pre-dose blood (plasma) and urine (clean catch) samples will be collected. At the time of TURBT on Day 5, one 3-mL blood (plasma) sample and a urine specimen will be collected for measurement of CPX-POM concentrations.

Patients will be followed for at least 30 days after the last dose of CPX-POM for safety.

4.2. Rationale for Study Design

The primary purpose of this study is to evaluate safety and dose tolerance as well as investigate the mechanisms of action of CPX-POM in patients with newly diagnosed or recurrent, untreated or intravesical treatment completed >6 months before the current diagnosis, resectable tumors, after administration of the recommended phase 2 dose (RP2D) to the target patient population. The patient population selected will have pre-dose tumor samples obtained by in-office cystoscopy available and will be scheduled for TURBT, and therefore will not need to undergo additional, study-specific, invasive procedures.

4.3. Dose Selection

The dose planned for administration to patients in this study is the MTD and RP2D that was determined during Study CPX-POM-001: 900 mg/m² once daily by 20 minute IV infusion for 5 days.

4.4. End of Study Definition

A patient is considered to have completed the study if he/she has completed 5 days of dosing with CPX-POM and has undergone TURBT from which tissue, blood, and urine samples are collected. Patients will also complete a Day 35 Follow-Up Visit.

The end of the study is defined as the date of the last procedure for the last patient in the study.

5. STUDY POPULATION

5.1. Inclusion Criteria

1. Patient is male or female aged ≥ 18 years.
2. Patient provided signed and dated informed consent prior to initiation of any study procedures.
3. Patient is likely to have a new bladder tumor based on clinical presentation or is at high risk for tumor recurrence based on previous history.
4. Patient has a cystoscopically confirmed bladder tumor and will be scheduled to undergo TURBT.
5. Patient has not received prior treatment for bladder cancer or completed their last intravesical therapy >6 months before screening.
6. Patient has an ECOG performance status of 0 (fully active, able to carry out all pre-disease activities without restriction) or 1 (unable to perform physically strenuous activity but ambulatory and able to carry out work of a light or sedentary nature).
7. Patient has a predicted life expectancy of ≥ 3 months.
8. Patient has adequate renal function (creatinine $\leq 1.5 \times$ the upper limit of the normal range (ULN) or an estimated glomerular filtration rate (eGFR) of >30 mL/min/1.73 m²).
9. Patient has adequate hepatic function, as evidenced by a total bilirubin $\leq 1.5 \times$ ULN, aspartate aminotransferase (AST) $\leq 3 \times$ ULN and /or alanine aminotransferase (ALT) $\leq 3 \times$ ULN
10. Patient has adequate bone marrow function, as evidenced by hemoglobin ≥ 9.0 g/dL in the absence of transfusion within the previous 72 hours, platelet count $\geq 100 \times 10^9$ cells/L, and absolute neutrophil count (ANC) $\geq 1.5 \times 10^9$ cells/L.
11. Patient has no significant ischemic heart disease or myocardial infarction within 6 months before the first dose of CPX-POM and currently has adequate cardiac function, as evidenced by a left ventricular ejection fraction of $>50\%$ as assessed by multi-gated acquisition (MUGA) or ultrasound/echocardiography (ECHO); and corrected QT interval by Fridericia's correction formula (QTcF) <450 msec for males and <470 msec for females. The eligibility of patients with ventricular pacemakers for whom the QT interval may not be accurately measurable will be determined on a case-by-case basis by the Sponsor in consultation with the Medical Monitor.

12. Patient and his/her partner agree to use adequate contraception after providing written informed consent through 3 months after the last dose of CPX-POM, as follows:
 - a. For women: Negative pregnancy test during Screening and at Day 1 of each treatment cycle and compliant with a medically-approved contraceptive regimen during and for 3 months after the treatment period or documented to be surgically sterile or postmenopausal.
 - b. For men: Compliant with a medically-approved contraceptive regimen during and for 3 months after the treatment period or documented to be surgically sterile. Men whose sexual partners are of child-bearing potential must agree to use 2 methods of contraception prior to study entry, during the study, and for 3 months after the treatment period.
13. Patient is willing and able to participate in the study and comply with all study requirements.

5.2. Exclusion Criteria

Patients who meet *any* of the following exclusion criteria are not to be enrolled in this study.

1. Patients received prior intravesical therapy for bladder cancer within ≤ 6 months of the current diagnosis.
2. Patients must not have had any of the following within 6 months before study drug administration:
 - a. Myocardial infarction
 - b. Severe/unstable angina
 - c. Symptomatic congestive heart failure
 - d. Cerebrovascular accident or transient ischemic attack, or
 - e. Pulmonary embolism
3. Ongoing cardiac dysrhythmias of National Cancer Institute (NCI) Common Terminology Criteria for Adverse Events (CTCAE) Version 4.03 grade 2.
4. Evidence of NYHA functional class III or IV heart disease.
5. Uncontrolled hypertension ($>150/100$ mmHg despite optimal medical therapy).

6. Patient has an uncontrolled or severe intercurrent medical condition. The decision to exclude a patient from the study for an uncontrolled or severe intercurrent medical condition will be made by the Principal Investigator. Examples could include epilepsy, resistant infection, or any other neurological disease that would make clinical assessment difficult.
7. Patient underwent major surgery or radiation therapy within 4 weeks before the first dose of CPX-POM or received an investigational drug or device within 4 weeks or 5 half-lives of that agent (whichever is shorter) before the first dose of CPX-POM. A minimum of 10 days between termination of the investigational drug and administration of CPX-POM is required.
8. If female, patient is pregnant or breast-feeding.
9. Patient has evidence of a serious active infection (e.g., infection requiring treatment with IV antibiotics).
10. Patient has a known, active Hepatitis A infection.
11. Patient has known human immunodeficiency virus (HIV) or Hepatitis B, or C infection, as such patients may be at increased risk for toxicity due to concomitant treatment and disease-related symptoms may preclude accurate assessment of the safety of CPX-POM.
12. Patient has an important medical illness or abnormal laboratory finding that, in the Investigator's opinion, would increase the risk of participating in this study.
13. Patient is taking warfarin.
14. Patients may not have another malignancy that could interfere with the evaluation of safety or efficacy of the study drug. Patients with a prior malignancy will be allowed without approval in the following circumstances:
 - a. Not currently active and diagnosed at least 3 years prior to the date of registration.
 - b. Non-invasive diseases such as low risk cervical cancer or any cancer in situ.
 - c. Localized (early stage) cancer treated with curative intent (without evidence of recurrence and intent for further therapy), and in which no chemotherapy was indicated.(e.g., low/intermediate risk prostate cancer, etc.).
 - d. NMIBC for which treatment was completed >6 months before the current diagnosis.
15. Patient has known allergy or hypersensitivity to any component of CPX-POM.
16. Patient is taking any iron replacement therapy administered IV, intramuscularly, or orally due to the potential for loss of anticancer activity due to drug and/or metabolites chelating iron.

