9.5.2. Laboratory Evaluations

Summaries of clinical laboratory data will be provided using descriptive statistics. No inferential statistics will be provided. Quantitative values and change from baseline in quantitative values will be summarized by dose group. Listings of all laboratory results and reference ranges will be provided.

Graded laboratory abnormalities will be defined using the grading scheme based on NCI CTCAE (4.03). The incidence of treatment-emergent laboratory abnormalities, defined as values that increase at least one toxicity grade from baseline at any time post baseline up to and including the date of last dose of study drug, will be summarized by treatment group. If baseline data are missing, then any graded abnormality (i.e., at least a Grade 1) will be considered treatment emergent.

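### Exclusion 3, as printed, bars ongoing cardiac dysrhythmia of CTCAE grade 2 but not of any more severe grade

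*Protocol*

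**What the plan says.** Protocol Section 5.2 states that patients who meet any "of the following exclusion criteria are not to be enrolled in this study". Each exclusion therefore works on its own, as a yes-or-no test.

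Exclusion 3 is the rhythm criterion: "Ongoing cardiac dysrhythmias of National Cancer Institute (NCI) Common Terminology Criteria for Adverse Events (CTCAE) Version 4.03 grade 2". The sentence ends there, with no comparison sign and no phrase such as *or higher*.

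The next criterion, exclusion 4, reads "Evidence of NYHA functional class III or IV heart disease" and so covers the severe end of its scale by name.

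Two general exclusions rest on judgement. Exclusion 6 begins "Patient has an uncontrolled or severe intercurrent medical condition" and leaves the decision to the Principal Investigator. Exclusion 12 reads "Patient has an important medical illness or abnormal laboratory finding that, in the Investigator's opinion, would increase the risk of participating".

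The SAP does not restate the eligibility criteria, and no other part of the protocol gives exclusion 3 with a different bound.

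**The concern.** A severity-based exclusion normally bars a level and everything worse. This one bars a single level. Applied as printed, it turns away the milder condition and lets the more severe one through, and no design purpose in the documents would explain that.

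The primary objective is safety and dose tolerance at the dose that Protocol Section 4.3 identifies as the MTD. Eligibility is checked at Screening and again on Day 1 (Table 1). A line-by-line check of exclusion 3 would record a patient with a grade above 2 as not meeting it. A grade 2 patient would fail and, under Section 5.4, could not be rescreened. What is at stake is the protection of patients at entry and the consistency of eligibility and deviation records.

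**Working it through.** No arithmetic applies, and the plan states no figure on this point. The check is a comparison of texts, in four steps.

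**1. Does a higher grade mean a worse event in this protocol?** Yes. Section 2.1 reports Grade 3 confusion as dose limiting, whereas Grade 1 confusion at 600 and 900 mg/m² was not. Section 9.5.2 counts a laboratory value as treatment-emergent when it rises by at least one toxicity grade.

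**2. How does the protocol write an open-ended threshold when it means one?**

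| Place | Wording | Form |
|---|---|---|
| Section 2.2 | "grade \geq 2 hearing loss" | sign before a grade (it came through as a typesetting code) |
| Section 9.5.2 | "any graded abnormality (i.e., at least a Grade 1) will be considered treatment emergent" | bound spelled out in words |
| Section 5.2, exclusion 4 | "Evidence of NYHA functional class III or IV heart disease" | upper classes listed |
| Section 5.2, exclusion 3 | "Ongoing cardiac dysrhythmias of National Cancer Institute (NCI) Common Terminology Criteria for Adverse Events (CTCAE) Version 4.03 grade 2" | single grade, no bound |

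Exclusion 3 is the odd one out.

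**3. Was a sign lost when the PDF was read?** The same list keeps its signs in exclusion 1, "Patients received prior intravesical therapy for bladder cancer within ≤ 6 months of the current diagnosis", and in exclusion 5 (blood pressure above 150/100 mmHg). Section 5.1 keeps several, and Section 2.2 keeps one directly before a grade. Loss at this one place is possible but unlikely.

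**4. Does another criterion catch a grade above 2?**

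| Criterion | What it tests | Rhythm or dysrhythmia grade named? |
|---|---|---|
| Inclusion 11 | ischemic heart disease or infarction, ejection fraction, QTcF | No; patients with ventricular pacemakers whose QT cannot be measured accurately are decided case by case |
| Exclusion 2 | infarction, angina, symptomatic heart failure, stroke or TIA, pulmonary embolism, all within 6 months | No |
| Exclusion 4 | NYHA class | No |
| Exclusion 6 | severe intercurrent illness; the examples given are neurological disease and infection | No; investigator's decision |
| Exclusion 12 | important illness or laboratory finding that raises risk | No; investigator's opinion |

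Read literally, exclusion 3 is met at grade 2 and not met above it, and no other objective criterion tests rhythm.

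**The case against.** The strongest reply is that no such patient would be enrolled in practice. A serious ongoing dysrhythmia fits naturally within exclusions 6 and 12. The investigator applying them would have rhythm data, since screening includes triplicate 12-lead ECGs, MUGA or ECHO, and chest imaging. Inclusion 11, exclusions 2 and 4 and the ECOG 0 or 1 requirement would remove some of these patients for other reasons. Many clinicians would also read the criterion as including higher grades. This stands as far as it goes: the documents do not show that the wording would admit anyone. It does not repair the rule. The sponsor gave dysrhythmia its own graded criterion, and a discretionary catch-all does not make that criterion correct.

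A second reply is that the whole point turns on one missing character in text read from a PDF. That is fair, and it makes checking the source page the first step. The signs that survive elsewhere make loss unlikely but do not rule it out.

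A reader might also infer that, with about 12 patients, one wrongly admitted patient could drive the cardiac adverse event and ECG results. The documents do not support this. Every patient carries the same share of a set that size, so the share says nothing about this criterion. Under Protocol Section 8.1.1.1, a condition present before screening that does not worsen is not an adverse event. SAP Section 9.4 limits the summaries to events after first dosing and existing events that worsened. SAP Section 9.8 presents ECG interpretation as shifts from baseline, and ECG parameters both at each time point and as change from baseline. A stable dysrhythmia at entry would be part of the baseline; only worsening would count as treatment-emergent. Protocol Section 2.1 also reports no ECG abnormality in the earlier study at doses up to 1200 mg/m².

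**Conclusion.** The point holds as a wording error in an operative eligibility rule: the only objective rhythm criterion is stricter for grade 2 than for anything worse. It should be corrected because it concerns entry to a safety study and costs almost nothing to put right.

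Its size cannot be put as a number. The documents give no frequency of ongoing dysrhythmia above grade 2 in this population. No estimate, sample size or error rate changes; SAP Section 4 states that there was no formal sample size calculation.

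The conclusion assumes that the extracted text matches the printed page and that the criterion is applied as written. If a comparison sign is present in the source, the point falls away.

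**What to change.** First, check exclusion 3 on the source page for a comparison sign. If there is none, the sponsor should confirm which grades it meant to exclude and amend the criterion to state that range explicitly, so that no grade is barred while a more severe one passes. The choice of range is the sponsor's clinical decision, and none is proposed here. The eligibility CRF check should carry the same wording.

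The cost is a one-phrase protocol amendment and a matching edit to the CRF check. It needs no added patients, procedures or analyses.

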5.3. Meals and Dietary Considerations

There are no meal or dietary restrictions.

5.4. Screen Failures

Patients who fail inclusion and/or exclusion criteria may not be rescreened for the study.

6. TREATMENTS

6.1. Investigational Product

6.1.1. Description of Investigational Product

Fosciclopirox or ciclopirox prodrug (CPX-POM), sodium ((6-cyclohexyl-4-methyl-2-oxopyridin-1(2H)-yl) oxy) methyl phosphate, is the phosphoryloxymethyl ester of CPX. CPX-POM will be provided as a sterile liquid formulation for IV administration.

6.1.2. Packaging and Labeling

CPX-POM will be packaged in plastic, 10-mL vials containing CPX-POM 50 mg/mL solution. Vials will be labeled according to applicable regulatory requirements.

6.1.3. Storage and Handling

CPX-POM vials must be stored under refrigerated conditions at 2 to 8 °C.

Only patients enrolled in the study may receive CPX-POM and only authorized site staff may supply or administer CPX-POM. All CPX-POM must be stored in a secure, environmentally controlled, and monitored (manual or automated) area in accordance with the labeled storage conditions with access limited to the investigator and authorized site staff.

6.1.4. Dosage and Administration

At baseline, the body surface area (BSA) will be calculated by the Dubois method using Screening height and baseline weight measurements. The baseline BSA is to be used to determine the patient's study drug dose.

$$\text{Dubois Formula: } \text{BSA} = 0.007184 \times W^{0.425} \times H^{0.725}$$

CPX-POM will be administered as an IV infusion once daily on Days 1-5 of the study. CPX-POM will be added to a 100-mL piggyback bag of 0.9% sodium chloride solution and infused over a 20-minute period. The dose administered will be 900 mg/m².

